4.2.3 Secondary Outcome Measure #3 – Premature Discontinuation of HCV medications

Measure Title: Percentage of Participants who Prematurely Discontinued HCV Study Medications

Measure Description: Premature discontinuation was defined by participant self-report, as there were no planned clinic visits during the 12 week study medication period. Participants discontinuing study follow-up without information about completion of HCV study medications were counted as having prematurely discontinued medications.

A two-sided, 95% confidence interval was calculated for the percentage using the Wilson (score) method.

Time Frame: From treatment initiation to SVR12 evaluation.

Population Description: Participants who enrolled into study and received first dose of study medication.

Associated study objective: “To estimate the proportion of participants who prematurely discontinue HCV treatment.”

Details: Since participant reporting of the timing of stopping study treatment may be by participant recall more than 12 weeks after the fact, premature discontinuation will be defined by the final treatment dose date being fewer than 11 weeks (or fewer than 77 days) post initial dose accounting for reported treatment interruptions. The timing and reasons for premature discontinuation will be summarized, as those details are available in the study database. As available, any other details on the disposition of study treatment (e.g. treatment interruptions), will be summarized.

4.3 Other Outcome Measures

4.3.1 Types of evaluations at unplanned clinic visits

This will be a descriptive analysis to summarize the nature of evaluations at unplanned clinic visits, e.g. whether and number of lab tests.

4.3.2 Prevalence of HCV resistance-associated substitutions (RASs) among participants who do not achieve SVR [if RAS data are available at time of analysis report]

Measure Title: *Percentage of Participants with HCV resistance-associated substitutions (RASs) among non-SVR Participants*

Measure Description: *HCV resistance-associated substitutions (RASs) were defined as amino acid substitution that confer reduced susceptibility to a direct-acting antiviral (DAA) and may contribute to virology failure. Non-SVR responders were assessed for RASs by comparing SVR12 sequence data with baseline to assess amino acid changes in the NS5A and NS5B gene regions.*

Time Frame: *At time of SVR12 evaluation.*

Population Description: *Participants who do not achieve SVR.*

Associated study objective: *“To estimate the prevalence of HCV resistance-associated substitutions (RASs) among participants who do not achieve SVR.”*

Details: Those who do not achieve SVR with an observed HCV RNA >LLOQ will have both baseline and SVR specimens tested for HCV RASs by sequencing the NS5A and NS5B regions. Participants in this sub-set with HCV RASs present in their SVR specimen that were not present in their baseline specimen will be enumerated along with the relative frequencies of new RASs. A description of the observed RASs will also be provided.

Note: This outcome will only be included in the analysis report if data on RASs is available to the statistician and ready for analysis.

5 Statistical Principles

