10.2 Outcome Measures

10.2.1 Primary Outcome Measures

- 10.2.1.1 Efficacy: Sustained virologic response defined as <LLOQ of HCV RNA in plasma from the earliest sample drawn at least 22 weeks following study entry. Missing results will be treated as SVR non-responders.
- 10.2.1.2 Safety: SAEs as defined by International Council for Harmonization (ICH) guidelines occurring from study entry until 24 weeks following study entry.

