10.2.3 Other Outcome Measures

- 10.2.3.1 HCV reinfection defined as detectable HCV RNA and HCV sequence from subsequent to evaluation of SVR response, distinct from the baseline sequence and defined only among SVR responders
- 10.2.3.2 Change in FIB-4 between study entry and final study evaluation, defined only among SVR responders
- 10.2.3.3 Treatment emergent RASs among SVR non-responders
- 10.2.3.4 Quality of life (health related utility) before and after HCV cure
- 10.2.3.5 Cost per SVR attained- both globally and stratified by country - calculated using country-specific costs and expressed in US\$ 2017.
- 10.2.3.6 Mode of remote participant contact over time

10.2.3.7 Number and timing of unplanned visits, number of types of evaluations at unplanned visits

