3.3.2 Secondary Objectives

1. To estimate the proportion of participants with unplanned clinic visits prior to SVR evaluation.
2. To summarize the occurrence of adverse events, other than SAEs, within 24 weeks following study entry.
3. To estimate the proportion of participants who prematurely discontinue HCV treatment.

3.3.3 Exploratory Objectives (only the objectives addressed in the primary analysis are listed here)

1. *To describe the number and types of evaluations performed at unplanned visits.*
2. *To estimate the prevalence of HCV resistance-associated substitutions (RASs) among participants who do not achieve SVR [if data available].*

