4.1 Primary Outcome Measures

4.1.1 Primary Efficacy Outcome Measure

Measure Title: *Percentage of Participants with Sustained Virologic Response 12 (SVR12)*

Measure Description: *SVR12 was defined as plasma HCV RNA less than the lower limit of quantification (LLOQ) from the earliest sample drawn at least 22 weeks following study treatment initiation (i.e. at a visit scheduled at least 10 weeks after scheduled end of study treatment). Participants without any HCV RNA result at least 22 weeks after treatment initiation will be considered as having HCV RNA greater than the LLOQ.*

A two-sided 95%, confidence interval was calculated for this percentage using the Wilson (score) method.

Time Frame: *At least 22 weeks and up to 76 weeks from treatment initiation.*

Population Description: *Participants who enrolled and received first dose of study medication.*

Associated study objective: *“To estimate SVR (defined as HCV RNA < lower limit of quantification [LLOQ] at least 10 weeks after the end of treatment [EOT] [which is at least 22 weeks from the study entry visit date]).”*

Details: Due to the definition of SVR outcome measure, missing HCV RNA results will lower the overall percentage of participants with SVR. Therefore, various reasons for non-SVR (e.g., discontinued treatment early due to various reasons including intolerance, observed HCV RNA \geq LLOQ, missing evaluation for SVR (and reasons as known), and the number of participants meeting each reason for non-SVR, will be presented in order to interpret the overall SVR sample estimate.

For interim analyses: Interim analysis is planned when SVR outcomes are available for approximately 100 participants. At interim reviews, SVR will be calculated only among those with potential to contribute to SVR (by having at least 22 weeks elapsed since study entry). Imputation of missing SVR evaluation as non-SVR response will only occur for participants for whom more than 76 weeks since study enrollment has elapsed. In other words, early study discontinuations prior to week 22 will not be counted in SVR estimation at interim review, as these could bias the estimation of SVR towards futility. Instead, these early study discontinuations prior to week 22 (before available for SVR evaluation), and others missing SVR evaluation, will contribute to the interim monitoring

trigger. For more details, refer to Overview of Formal Interim Monitoring of section 3.5 above.

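### The RAS measure in SAP 4.3.2 names one denominator and tests another, and it counts only new substitutions although the objective is prevalence

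*SAP*

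**What the plan says.** **Objective.** Protocol 1.4.3 and SAP 3.3.3 share the same aim: "To estimate the prevalence of HCV resistance-associated substitutions (RASs) among participants who do not achieve SVR".

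**Title and population.** SAP 4.3.2 titles the measure "Percentage of Participants with HCV resistance-associated substitutions (RASs) among non-SVR Participants" and gives the population as "participants who do not achieve SVR", without restricting it to people who were tested.

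**Who is non-SVR.** SAP 4.1.1: "Participants without any HCV RNA result at least 22 weeks after treatment initiation will be considered as having HCV RNA greater than the LLOQ". Protocol 10.2.1.1: "Missing results will be treated as SVR non-responders".

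**Who is tested and counted.** The Details of SAP 4.3.2: "Those who do not achieve SVR with an observed HCV RNA >LLOQ will have both baseline and SVR specimens tested for HCV RASs". The next sentence confines the count to that tested group. It counts participants whose SVR-visit specimen carries a RAS that the baseline specimen lacked, and adds the relative frequencies of new RASs. The observed RASs are also to be described, with no percentage attached. Protocol 10.6.3 reads the same way, except that it includes results at or above LLOQ where the SAP says above.

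**Protocol outcome.** Section 10.2.3.3 names the outcome "Treatment emergent RASs among SVR non-responders".

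**Status.** The measure is exploratory, and is reported only if RAS data are ready when the analysis report is written.

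**The concern.** Two separate questions are left open.

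The first is the denominator. A participant counted as non-SVR only because the result is missing belongs to the titled population but can never enter the numerator. If that population is used, the percentage combines resistance among virologic failures with the rate of missed SVR visits. The SAP deals with the same problem elsewhere: the populations in 4.1.2 and 4.2.2 are limited to participants with some post-entry adverse event evaluation. Section 4.3.2 has no such limit.

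The second is the numerator. Prevalence of RASs at failure includes substitutions that were there before treatment. A count of new RASs leaves out any participant whose only RASs were already present at baseline. The two quantities answer different questions, and only the second is specified.

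What is at stake is how one exploratory result is read. Two analysts could follow the SAP faithfully and report different percentages under the same title, and neither percentage would be the one the objective asks for.

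**Working it through.** The documents give no expected RAS rate, count or precision, so there is no planned figure to reproduce. The check compares the texts and then sizes the effect on assumed counts.

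**1. Denominator, by source**

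| Source | Group |
|---|---|
| SAP 4.3.2, Title and Population | all non-SVR, including missing results |
| SAP 4.3.2, Details | non-SVR with observed HCV RNA above LLOQ |
| Protocol 10.6.3 | non-SVR with observed HCV RNA at or above LLOQ |
| Protocol 6.3.14 | SVR non-responders, with no stated restriction |

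SVR requires a value below LLOQ, so a result exactly at LLOQ is non-SVR. The SAP Details would leave it untested, while protocol 10.6.3 would test it. SAP 4.1.1 itself uses at or above LLOQ when it lists reasons for non-SVR.

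**2. Effect of the denominator**

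Let N be all non-SVR participants, m those with a missing result, V = N − m those sequenced (assuming every viraemic specimen yields a sequence), and k those counted with a RAS. Then

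k/N = (k/V) × (V/N),

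so the dilution factor is V/N. For scale, N = 29 is the smallest non-responder count that meets the LOW benchmark and N = 8 the largest that meets the HIGH benchmark (protocol Table 10.4-1). The value m = 20 is the most non-evaluable participants allowed before an unplanned review is triggered (protocol 10.5.1, SAP 3.5). The other values of m are assumptions.

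| N | m | V | V/N |
|---|---|---|---|
| 29 | 0 | 29 | 1.00 |
| 29 | 4 | 25 | 0.86 |
| 29 | 10 | 19 | 0.66 |
| 29 | 20 | 9 | 0.31 |
| 8 | 4 | 4 | 0.50 |

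If the tested group is the denominator, the factor is 1 whatever m is.

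**3. Denominator and numerator varied separately**

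All RAS counts here are assumed.

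| Case (N = 29) | Counted | Over sequenced | Over all non-SVR |
|---|---|---|---|
| m = 10, V = 19 | any RAS, 14 | 14/19 = 73.7% | 14/29 = 48.3% |
| m = 10, V = 19 | new RAS only, 7 | 7/19 = 36.8% | 7/29 = 24.1% |
| m = 20, V = 9 | any RAS, 6 | 6/9 = 66.7% | 6/29 = 20.7% |
| m = 20, V = 9 | new RAS only, 3 | 3/9 = 33.3% | 3/29 = 10.3% |

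Reading across a row shows the denominator effect alone. Reading down within a case shows the numerator effect alone. The numerator effect depends on how many participants have only pre-existing RASs, which the documents do not give. If there are none, the counts of new and of any RAS coincide. If that describes every participant with a RAS, the count of new RASs is zero.

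Precision is poor on any definition: for 14/19 the 95% Wilson interval is 51.2% to 88.2%.

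**The case against.** The Details can fairly be read as settling the denominator. They limit testing to observed viraemia, count within that group, and speak of relative frequencies there. Protocol 10.6.3 matches. On that reading missing HCV RNA results dilute nothing. This stands as a plausible reading, but the Title and Population Description still say otherwise and no sentence ranks one above the other. The separate Analysis Implementation Plan may resolve it, but it is not among the documents reviewed.

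A reader might infer that the prevalence cannot be estimated at all. The documents do not support that. Baseline and SVR-visit specimens are both sequenced and the observed RASs are described, so prevalence among sequenced failures can be computed from planned data. What is missing is a defined percentage.

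A reader might also infer that the SAP departs from the protocol by counting new RASs. It does not: protocol 10.2.3.3 specifies treatment-emergent RASs. The mismatch is between objective and outcome, and it already exists within the protocol.

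Nor do the documents show that the percentage would mostly reflect loss to follow-up. SVR can be assessed up to week 76 (SAP 4.1.1), protocol 2.2 adds an incentive for attending the SVR visit, and the number with each reason for non-SVR, missing evaluation included, will be tabulated (SAP 4.1.1, protocol 10.6.1). Most of the count of non-responders not sequenced is therefore already planned; sequencing failures would be the addition.

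Finally, baseline RASs among failures cannot show whether such RASs predict failure, because RAS testing is planned only for non-responders. That limits what a baseline row can say. It remains a descriptive figure that separates pre-existing from emergent resistance.

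**Conclusion.** The point holds as an inconsistency to reconcile. SAP 4.3.2 leaves its denominator open between all non-SVR participants and those with observed viraemia. It also defines no percentage that answers the prevalence objective.

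Dilution is conditional. It arises only if the titled population is used, and its factor is V/N: 0.86 to 0.31 for 4 to 20 missing among an assumed 29 non-responders, and 1.00 on the Details reading. The shortfall from counting only new RASs cannot be sized from the documents and could be nil. All RAS counts above are illustrations, and V = N − m assumes that no sequencing attempt fails.

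Importance is low. The outcome is exploratory, descriptive and conditional on data availability. The primary SVR estimate, the sample size and the error rates are untouched.

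**What to change.** In SAP 4.3.2:

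1. Set the population to SVR non-responders with observed HCV RNA at or above LLOQ and usable NS5A/NS5B sequences, and use the same wording in Title, Population Description and Details.
2. On that denominator, report three separate percentages: RAS at baseline, any RAS at the SVR visit, and new RAS at the SVR visit. The second answers the objective, and the third keeps the protocol's treatment-emergent outcome.
3. State how many non-responders were not sequenced, separating missing SVR results from specimens without a usable sequence.
4. Change the SAP's above-LLOQ condition to at or above LLOQ, to agree with protocol 10.6.3.

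The cost is SAP wording and two extra rows in one table. No new specimens, assays or visits are needed, because both specimens are already to be sequenced.

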5.1 General Considerations

5.1.1 Definitions

Baseline: Any characteristic measured or evaluated prior to the first dose of study medication (including information collected at screening) can be used as a ‘baseline’ characteristic. Areas where use of screening could induce bias (due to eligibility criteria) will be noted in any analysis, as applicable.

SVR: Target not detected (TND) result is a valid that also qualifies as <LLOQ and will be counted as an SVR responder. When handling of multiple HCV RNA results, the valid result from the earliest sample drawn within the SVR evaluation window (starting 22 weeks post study treatment initiation) will be used for analysis.

Reference Start Dates:

- Study enrollment date: Date participant was enrolled on study.
- Treatment start date: Date participant took first dose of study treatment.

5.1.2 Clinic Study Visit Windows

MINMON intervention EPOCH [Step 1]: The first follow-up clinic visit at study week 24, for primary outcome SVR evaluation has a window of -14 days to +28 days. If week 24 study visit is missed, this “primary SVR evaluation” visit can occur anytime up to study week 72 which is the end of study follow-up.

Post SVR, post MINMON, or follow-up EPOCH [Step 2]: Two clinic visits are scheduled post SVR at week 48 and 72. The ranges of week 48 clinic visits were examined and the observed range is used for visit window; weeks 48 has a window of -28/+60 days. Week 72 has a window of \pm 28 days.

5.1.3 Analysis Sets

Enrolled participants who do not start study medication will be excluded from all analyses. Note that per protocol instructions, the first dose of study medication is to be observed in the study clinic during the entry evaluation visit.

Full analysis sample (= Efficacy analysis sample at final analysis): Participants who started study medication. For the efficacy analysis sample for interim reviews, refer to section: 4.1.1 Primary Efficacy Outcome Measure. At interim analyses, the efficacy analysis sample will differ from the full analysis sample as follows: participants missing HCV RNAs for SVR evaluation will not be counted as SVR non-responders unless they enrolled more than 76 weeks prior to dataset finalization. Thus, the efficacy analysis sample at interim reviews will be based on observed HCV RNAs in the SVR evaluation window plus participants who both left the study without a result for SVR evaluation and who enrolled more than 76 weeks ago (and thus can no longer be evaluated for SVR on study).

Safety analysis sample: Participants who started study medication and who were evaluated for AEs for the time period after first dose of study treatment through up to 24 week later. This criterion will be met for any participant having an unscheduled visit prior to week24/SVR evaluation, or any participant having a week 24 or SVR evaluation visit. At interim analysis, due to no planned study clinic visits prior to study week 24, this analysis sample include all participants who started treatment, and only exclude those who were both known lost to all follow-up and without any follow-up for AEs. This sample will be split into subgroups defined by those having week 24/SVR evaluation visit versus not.

5.1.4 Analysis Approaches

The analysis of each objective addressed in this SAP will be conducted using the appropriate analysis sample as defined in section 4.1.

As this is a single arm study, the primary descriptive and statistical inference on outcomes will be performed on the entire specified analysis sample as a single group, and focus on estimation. However, as there exist key subgroups upon which separate estimates for outcomes is desired, analyses will often (as specified below) be repeated within subgroups defined by the following:

- **Country** (to help inform each MOH or other, policy groups, as well as serving as an imperfect surrogate for HCV genotype)
- **Cirrhosis status** (compensated cirrhotic and non-cirrhotic by classification by FIB-4 score)
- **HIV-1 infection status** (positive and negative)
- **Sex assigned at birth** (female and male)
- **If data are available, by HCV genotype**

However, there are no plans to perform formal hypothesis testing for differences in outcomes among subgroups.

All statistical hypothesis testing at final analysis, will use the nominal significance level of 0.05. See detailed specifications at interim reviews for alternative significance levels.

6 Report Contents

Detailed descriptions of the content of each of the following sections are given in the AIP:

1. CONSORT Diagram (final analysis only)
2. Accrual
3. Baseline characteristics
4. Study conduct
 - a. Study status and follow-up
 - b. Study medication disposition
 - c. Remote contact at week 4
 - d. Adherence of medication, premature discontinuation of study treatment
 - e. Remote contact at week 22
 - f. Data and specimen availability (other than for SVR evaluation)
 - g. Unplanned Clinic Visits (number/reasons)
5. Safety
 - a. Primary Safety Outcome Measure: SAEs within 24 weeks
 - b. Secondary Safety Outcome Measure: other AEs within 24 weeks
 - c. Summary of other AEs (all AEs after 24 weeks)
 - d. Summary of pregnancies that occur during study participation
 - e. Summary of HIV-1 RNA among PLWH at Week 24/SVR visit
6. Efficacy
 - a. Study visit of SVR collection
 - b. SVR12 estimation
 - i. Summary of details (e.g assay, LLOQ, lab) used to evaluate SVR
 - ii. Estimation within subgroups
 - iii. Reasons for non-SVR
 - iv. Summary of participants not achieving SVR (baseline characteristics, study/treatment disposition, safety and tolerability information)
 - c. Summary of HCV RASs among participant not achieving SVR [if data available]
